7.2.16 Lymphocyte Subsets

Immunophenotyping by flow cytometry to monitor peripheral blood changes in lymphocytes (B, T and natural killer [NK] cells), leukocyte populations (leucocytes, lymphocytes, monocytes, and granulocytes), T cells subsets, T cells activation markers as well as potential drug resistance mechanisms (T cells exhaustion markers, Tregs and immune checkpoint ligands) will be completed. Lymphocyte subsets will be collected at time points outlined in the Schedule of Assessments (Table 9).

If B-cell counts have not recovered at the SFU visit (recovered is defined as number of CD19-positive cells per μL is 90 to 570), another sample will also be taken 6 months (+3 months) after SFU visit for determination of lymphocyte subsets.

7.2.17 Peripheral Blood Cytokines/Markers

To monitor activation of immune effector cells and better understand T cell activation, blood samples will be taken at various time points as indicated in the Schedule of Assessments (Table 9). Serum cytokines and chemokines will be measured.

7.2.18 Immunoglobulins

Immunoglobulins (IgG only) will be collected at time points outlined in the Schedule of Assessments (Table 9) to detect hypogammaglobulinemia or immunological changes.

7.2.19 Pharmacokinetic Assessments

If the subject consents to the intensive pharmacokinetics portion of this study, additional PK samples will be obtained. For intensive PK sample collection, serum samples will be collected for approximately 20 subjects at baseline and at scheduled time points during the treatment period within the first 2 treatment cycles. In cycle 1, samples will be taken prior to treatment start (prefer day 1, acceptable on day -1), and during infusion on day 1 (2 hours, 6 hours, 10 hours, ± 30 minutes), any time during day 2 and day 15 as well as on day 29 within 2 hours prior to the end of infusion and after the end of infusion at 3 hours (± 30 minutes) and 6 hours (± 30 minutes). In cycle 2, samples are collected at any time on day 2, day 15, and within 2 hours prior to end of infusion on day 29.

For non-intensive PK sample collection, 4 serum samples will be collected to measure blinatumomab serum concentration during the blinatumomab treatment period in all subjects who received the drug. PK samples will be collected on D2 and D15 in both cycle 1 and cycle 2 for determination of serum steady state drug concentrations (C_{ss}). Pharmacokinetic samples may be collected during the infusion at the same time that the other blood samples are collected. The samples will be measured with a validated assay.

PK samples must be drawn from a site that is distal from the site where the investigational product has been administered to avoid contamination of the PK samples and to better estimate PK parameters. On PK assessment days, the date and time of infusion bag changes and any dosing interruptions will be recorded in the eCRF.

7.2.20 Pregnancy Tests

Urine or serum pregnancy tests will be performed locally at each site on all females except for female subjects who are surgically sterile or ≥ 2 years post-menopausal. If the pregnancy test is positive at screening the subject should not be enrolled. If a standard of care pregnancy test is collected during the course of the study, and the result is positive, the investigator should contact the Amgen medical monitor for instructions.

If a female subject, or the partner of a male subject, becomes pregnant during the conduct of the study it must be reported on the Pregnancy and Lactation Notification Worksheet, ([Appendix C](#)).

7.3 Screening/Pre-treatment

Screening procedures are to be completed during the screening period at time points designated in the Schedule of Assessments ([Table 9](#)). In addition, the obligatory premedication ([Section 6.3](#)) will be administered during screening.

The screening process begins on the date the subject signs the IRB/IEC approved ICF and continues until enrollment. Informed consent must be obtained before completing any study specific procedures. Standard of care procedures such as bone marrow aspiration/biopsy and lumbar puncture are not considered study specific. Standard of care procedures may be performed prior to informed consent and used to determine eligibility, but must occur within 21 days prior to starting treatment with blinatumomab, unless specified otherwise.

Approved

Rescreening:

Subjects who are unable to complete or meet eligibility at the initial screening will be permitted to rescreen once, provided study recruitment has not closed. Upon signing a new ICF, a new 21-day screening window will begin. Subjects will retain the same subject identification number assigned at the original screening.

After reconsenting, all screening procedures, including the lumbar puncture and BM biopsy, must be repeated unless the procedure was performed within 14 days prior to treatment start.

7.4 Treatment

It is strongly recommended that subjects are hospitalized at least during the first 9 days (1 week plus 2 days following dose step) of the first cycle and the first 2 days of the following cycle. The hospitalization time depends on investigator's judgment, as well as safety and tolerability of blinatumomab. However, the hospitalization must span at least the first 2 days after treatment start in the first 2 cycles and after dose step. For cycle 3 and beyond, subjects will at least come in for an 8 hours outpatient observation followed by daily outpatient follow-ups during the subsequent 2 days. Additional hospitalization may be necessary, eg, in case of serious adverse events or restart of treatment after treatment interruptions due to adverse events (see [Section 6.5](#)).

7.4.1 Days of Infusion (Day 1 to Day 29, Applies to Each Treatment Cycle)

7.4.1.1 Prior to Infusion (D1)

Prior to infusion (D1), subjects have to complete all protocol-required procedures as per [Table 9](#). In addition, the obligatory premedication ([Section 6.3](#)) will be administered. Screening BM assessment sample has to be taken prior to treatment start or during the screening period. For subjects who interrupted treatment because of a CNS event grade 3, an MRI of the head must be performed (read locally) before a new treatment cycle will be started.

The results of the D1 laboratory tests taken prior to infusion start will not have to be available before starting treatment with blinatumomab. Assessments that were done within 24 hours prior to treatment start do not need to be repeated at D1 prior to infusion.

7.4.1.2 During Infusion (D1 to D28)

The infusion continues for 28 days, all protocol-required procedures and tests as per [Table 9](#) will be performed on D1 to D15 of each treatment cycle. In addition, the obligatory medication ([Section 6.3](#)) will be given. Replacement of infusion bags will be

performed as described in the IPIM. For the visits on D8, D15 there is a visit window of ± 1 day. Time window for all BM assessments is + 3 days during treatment phase.

7.4.1.3 End of Infusion (D29)

Protocol-required procedures and tests as per [Table 9](#) will be performed on D29 (end of infusion). For the visit on D29 there is a visit window of + 3 days.

7.4.2 Treatment Free Interval from Day 30 to Day 43 (D43 = D1 of sub-sequent cycle)

After each treatment cycle there will be a treatment free interval of 2 weeks before the next treatment cycle will be started. In exceptional cases, the treatment free interval may be extended by up to one week to accommodate hospital scheduling or patient travel. If the treatment will be continued with a further cycle, D43 corresponds to D1 of the following cycle, and the procedures and tests as per [Table 9](#) will be performed. In the final cycle to be administered if therapy is completed or discontinued, D43/D1 assessments will not be performed and the next visit will be the SFU visit.

7.5 Safety Follow-up Visit

All subjects, including subjects who withdraw early, should complete a SFU visit 30 days (± 3 days) after the last dose of protocol-specified therapy, or before HSCT/chemotherapy if applicable, or have discontinued the treatment of blinatumomab, whichever occurs first. The procedures per [Table 9](#) will be performed.

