In case of premature treatment discontinuation, the assessments planned for end of treatment (end of infusion) should be performed immediately. Exceptions: The CSF examination/prophylaxis does not have to be done in case of premature treatment discontinuation. Bone marrow aspiration/biopsy is not required in case of documented progressive disease. In addition, the SFU visit should be performed 30 days (± 3 days) after the last dose of blinatumomab was administered or, if applicable, before the start of non-protocol-specified therapy or alloHSCT, whichever occurs first. The subject should continue to come to all relevant long-term follow-up visits.

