9.2.2 Adverse Events

9.2.2.1 Reporting Procedures for Adverse Events That Do not Meet Serious Criteria

The investigator is responsible for ensuring that all adverse events observed by the investigator or reported by the subject that occur after protocol-required therapies through the SFU visit are reported using the Event eCRF. Adverse events related to obligatory pre-medication as well as adverse events related to study procedures during the screening period will be reported on the Event eCRF. If any other anti-leukemic therapy is started within 30 days after last administration of blinatumomab, subsequently only adverse events assessed as being related to blinatumomab will be reported. During the long-term follow-up period, only adverse events assessed as related to blinatumomab or study procedures will be recorded.

The investigator must assign the following adverse event attributes:

- Adverse event diagnosis or syndrome(s), if known (if not known, signs or symptoms),
- Dates of onset and resolution (if resolved),
- Severity [and/or toxicity per protocol],

- Assessment of relatedness to blinatumomab, and
- Action taken.

The adverse event grading scale used will be the CTCAE version 4.03. The grading scale used in this study is described in [Appendix A](#). The investigator must assess whether the adverse event is possibly related to blinatumomab. This relationship is indicated by a “yes” or “no” response to the question: Is there a reasonable possibility that the event may have been caused by investigational product (blinatumomab) or other protocol-required therapies?

The investigator must assess whether the adverse event is possibly related to any study-mandated activity (eg, administration of investigational product, protocol-required therapies, device(s) and/or procedure (including any screening procedure(s))). This relationship is indicated by a “yes” or “no” response to the question: “Is there a reasonable possibility that the event may have been caused by a study activity (eg, administration of investigational product, protocol-required therapies, device(s)), and/or procedure”?

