9.2.2.2 Reporting Procedures for Serious Adverse Events

The investigator is responsible for ensuring that all serious adverse events observed by the investigator or reported by the subject that occur during the entire study period including the screening period (from the signing of the informed consent) through the SFU visit are recorded in the subject’s medical record and are submitted to Amgen. All serious adverse events must be submitted to Amgen within 24 hours following the investigator’s knowledge of the event via the Event CRF.

Approved

If the electronic data capture (EDC) system is unavailable to the site staff to report the serious adverse event, the information is to be reported to Amgen via an electronic Serious Adverse Event Contingency Report Form within 24 hours of the investigator's knowledge of the event. See [Appendix B](#) for a sample of the Serious Adverse Event Worksheet/electronic Serious Adverse Event Contingency Report Form. For EDC studies where the first notification of a Serious Adverse Event is reported to Amgen via the electronic Serious Adverse Event Contingency Report Form, the data must be entered into the EDC system when the system is again available.

The investigator must assess whether the serious adverse event is possibly related to any study-mandated activity or procedure. This relationship is indicated by a "yes" or "no" response to the question: "Is there a reasonable possibility that the event may have been caused by a study activity/procedure"?

The investigator is expected to follow reported serious adverse events until resolution, stabilization of the condition, or until the subject is lost to follow-up.

New information relating to a previously reported serious adverse event must be submitted to Amgen. All new information for serious adverse events must be sent to Amgen within 24 hours following knowledge of the new information. The investigator may be asked to provide additional follow-up information, which may include a discharge summary or extracts from the medical record. Information provided about the serious adverse event must be consistent with that recorded on the Event eCRF.

If a subject is permanently withdrawn from protocol-required therapies because of a serious adverse event, this information must be submitted to Amgen.

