9.2.2.3 Reporting Serious Adverse Events After the Protocol-required Reporting Period

There is no requirement to monitor study subjects for serious adverse events following the protocol-required reporting period or after end of study. However, these serious adverse events can be reported to Amgen. In some countries, investigators are required to report serious adverse events that they become aware of after end of study. If serious adverse events are reported, the investigator is to report them to Amgen within 24 hours following the investigator's knowledge of the event.

Serious adverse events reported outside of the protocol-required reporting period will be captured within the safety database as clinical trial cases for the purposes of expedited reporting.

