Prior salvage regimens are those medications recorded on the prior anti-cancer therapies CRF where the line of therapy field indicates salvage chemotherapy.

Protocol-specified Therapy

Protocol-specified therapy refers to the treatment blinatumomab. The protocol also uses the term “protocol required therapy” but for consistency protocol-specified therapy will be used throughout this document.

Relative Treatment Duration of Blinatumomab:

For each cycle, the relative treatment duration will be duration of blinatumomab infusion for that cycle divided by 28 days, the planned duration of infusion. For the entire study, the relative treatment duration will be the duration of blinatumomab infusion for the entire study divided by 28 times the number of cycles started. Re-started cycles will count as 28 days for the period before the re-start and 28 days for the period after the re-start in the calculation of planned duration.

Study Day 1

The first day of the infusion of blinatumomab.

Treatment-emergent Adverse Event

AEs starting on or after first dose of blinatumomab as determined by the flag indicating if the adverse event started prior to the first dose on event page of CRF and up to and including 30 days after the end of blinatumomab. This reporting window also applies to treatment-emergent serious adverse events (SAEs).

7. Analysis Sets

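### SAE and disease-related-event collection ends at a movable follow-up visit instead of the SAP's 30 days, protocol 7.5 conflicts with 6.6 on the timing of that visit, and late related SAEs carry the weaker duty

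*Protocol*

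**What the plan says.** **When the SFU visit falls.** Protocol 7.5 gives 30 days (± 3) after the last dose, then adds "or before HSCT/chemotherapy if applicable, or have discontinued the treatment of blinatumomab, whichever occurs first". Section 6.6, which governs premature discontinuation, differs. At discontinuation "the assessments planned for end of treatment (end of infusion) should be performed immediately". Separately, "the SFU visit should be performed 30 days (± 3 days) after the last dose of blinatumomab was administered". Section 6.6 names only one ground for holding that visit sooner: "or, if applicable, before the start of non-protocol-specified therapy or alloHSCT, whichever occurs first". The synopsis, 3.1 and Table 9 give 30 days (± 3), and 3.5.1 gives an SFU period of about 4 weeks. Section 3.1 also asks that the visit be completed before a transplant.

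**What is collected until then.** DREs (9.2.1) and all-cause non-serious AEs (9.2.2.1) run through the SFU visit. So do SAEs (9.2.2.2): "including the screening period (from the signing of the informed consent) through the SFU visit are recorded". Section 9.2.2.1 limits reporting to blinatumomab-related events once other anti-leukemic therapy starts within 30 days of the last dose. Section 9.2.1 also requires a fatal DRE to be reported and gives no end date. Table 9 shows AE, SAE and DRE collection throughout the core study only.

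**What is collected afterwards.** Section 9.2.2.1, headed as covering events that do not meet serious criteria, says: "During the long-term follow-up period, only adverse events assessed as related to blinatumomab or study procedures will be recorded". Section 9.2.2.3 says: "There is no requirement to monitor study subjects for serious adverse events following the protocol-required reporting period or after end of study". It adds that such SAEs may be reported to the sponsor.

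**What is analysed.** SAP section 6 (Treatment-emergent Adverse Event) counts AEs and SAEs "up to and including 30 days after the end of blinatumomab". SAP 10.6.1 describes treatment-emergent events with no end date.

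**The concern.** The SAP counts events over a fixed number of days, while the protocol ends mandatory collection at a visit whose date can move. Whenever the visit comes early, the SAP counts days on which sites have no general duty to record SAEs or DREs. Incidence over those days would then depend on voluntary reporting.

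The subjects affected are not a random subset. They go early to other anti-leukemic therapy or to transplant, so they include treatment failures as well as responders bridged to alloHSCT.

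Safety is a stated objective of this single-arm trial, and the event burden in this disease is high. Protocol 2.5.2 reports SAEs in 64% and fatal treatment-emergent AEs in 14.8% of subjects in the earlier phase 2 study MT103-211. Under 9.2.2.5, serious DREs are generally not expedited individually and rely on review by the Data Review Team, which can review only what is collected.

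**Working it through.** **1. The plan's own period.** Section 3.5.1 gives a core study of up to 37 weeks: 3 (screening) + 5 × 6 = 30 (treatment) + 4 (SFU) = 37. This reproduces. Thirty days is 30/7 = 4.3 weeks, so the design intends about 30 days of safety follow-up, in line with SAP section 6.

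**2. SFU timing side by side.**

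| Source | Timing of the SFU visit after the last dose |
|---|---|
| Synopsis, 3.1, Table 9 | day 27 to 33 |
| 3.5.1 | about 4 weeks |
| 6.6 | day 27 to 33, or earlier if new therapy or alloHSCT starts |
| 7.5, literal | the earliest of day 27 to 33, HSCT/chemotherapy, and discontinuation |

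Under 7.5 the discontinuation limb always comes first. If the infusion stops at the decision to discontinue, it falls at about day 0. The treatment-free interval is at most 14 + 7 = 21 days, so a decision taken within it also precedes day 30.

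**3. Share of the SAP window without the general collection duty.** For a visit on day d, the share is max(0, 30 - d)/30.

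- Literal 7.5, d about 0: 30/30 = 100%.
- Regular visit, d = 27: 3/30 = 10%; d = 30 to 33: 0%.
- Early visit before new therapy or alloHSCT, with d assumed because the documents give no timing: day 7, 23/30 = 77%; day 14, 16/30 = 53%; day 21, 9/30 = 30%.

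These are shares for one subject, not for the trial.

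**4. What remains mandatory between an early SFU visit and day 30.**

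| Event | Duty after an early SFU visit |
|---|---|
| Related non-serious AE | Recorded (9.2.2.1) |
| Unrelated non-serious AE | None, by design once new anti-leukemic therapy starts |
| SAE, related or not | None on the natural reading (9.2.2.2, 9.2.2.3) |
| Non-fatal DRE | None (9.2.1) |
| Fatal DRE | Required, no end date stated (9.2.1) |

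Section 9.2.2.1 foresees new therapy within the 30 days and says what continues. Sections 9.2.1 and 9.2.2.2 have no matching provision.

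**5. Long-term follow-up.** The same comparison applies after a visit held on time: related non-serious AEs are recorded, and SAEs may be reported but need not be. Table 9 shows no AE or SAE collection in that period, which also conflicts with the long-term sentence in 9.2.2.1.

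**The case against.** **The 30-day window is intact.** The discontinuation limb in 7.5 does not parse as a visit time, and it nearly repeats the analysis-trigger wording of 10.3.3. Taken literally, it makes the 30-day limb of its own sentence redundant. Every other passage keeps about 30 days, and 6.6 puts only the end-of-treatment assessments at discontinuation. This stands. A reader might infer from 7.5 alone that the window is lost for everyone who discontinues; the documents taken together do not support that. What remains is a contradiction for sites to resolve.

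**Related SAEs are already covered.** The long-term sentence in 9.2.2.1 says adverse events without restricting them to non-serious ones. Section 9.1.3 defines an SAE as a kind of adverse event, and 9.2.2.2 asks for all SAEs within 24 hours of knowledge. Section 9.2.2.3 waives monitoring, not the handling of reports received. This is a fair alternative reading. Against it stand the heading of 9.2.2.1, the explicit SFU limit in 9.2.2.2 and the permissive wording of 9.2.2.3. The text is at best ambiguous.

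**Table 9 sets a period-based window.** Collection through a core study that includes about 4 weeks of SFU could be read as running to day 28 or so whatever the visit date. That competes with the visit-based wording in section 9 and shows that the two need aligning.

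**Deaths would still be seen.** A reader might infer that a fatal event after an early SFU visit goes unrecorded. Section 9.2.1 requires fatal DREs without an end date, Appendix D lists infection as a DRE, and SAP section 6 provides for death dates obtained after the end of study. That inference does not hold in general.

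**The loss could be sized from non-responders.** It is tempting to treat everyone without CR/CRh* as an early stopper. Under 3.1 and 6.6, subjects with 5% or fewer marrow blasts may continue, and the timing of next therapy appears nowhere. No trial-wide figure can be supported.

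**Conclusion.** The point holds in three parts of different strength.

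1. Section 7.5 contradicts 6.6, 3.1, 3.5.1 and Table 9 on the SFU visit. That it is a drafting slip is an inference, though a likely one. The contradiction itself is certain.
2. For subjects who go to new therapy or alloHSCT before day 30, mandatory SAE and non-fatal DRE collection ends before the window the SAP counts. This follows from 6.6 as well as 7.5, so correcting the slip does not remove it. The affected share of a subject's window ranges from 0 to 100%, depending on when next therapy starts.
3. After the SFU visit, related SAEs carry a weaker duty than related non-serious AEs. This rests on reading 9.2.2.1 in line with its heading.

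Reported SAE incidence could be understated, but by how much cannot be derived from the documents. The primary endpoint, sample size and alpha are untouched. The sponsor should make the change; it is not a bar to the trial's main conclusion.

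**What to change.** (a) Remove discontinuation as an SFU trigger in 7.5, so that it agrees with 6.6, 3.1, 3.5.1 and Table 9.

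(b) In 9.2.1, 9.2.2.1 and 9.2.2.2, end AE, SAE and DRE collection at the later of the SFU visit and 30 days after the last infusion, by telephone where the visit was earlier. This matches SAP section 6. Keep the existing limit to related events once new anti-leukemic therapy starts, and say whether alloHSCT counts as such therapy. After new therapy this change recovers related events only, and the protocol should acknowledge that.

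(c) State in 9.2.2.2 and 9.2.2.3 that related SAEs are reportable during long-term follow-up, as related AEs already are, and align the AE/SAE/DRE row of Table 9. Align SAP 10.6.1 with SAP section 6 on the end of the treatment-emergent window.

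The cost is protocol and SAP wording, one extra telephone contact for subjects with an early SFU visit, and possibly a slightly higher reported SAE incidence.
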